5.7.4. Analyses of Other Secondary and Exploratory Efficacy Variables

Other secondary efficacy endpoints will be analyzed by type of endpoint defined in Sections 4.5.2 to 4.5.8 for all cohorts. The analysis methods for key secondary efficacy endpoints in both cohort A and cohort B will also be applied to exploratory endpoints in both cohort A and cohort B if appropriate. Otherwise, the primary approach to the data will be descriptive statistics. For the comprehensive evaluation of efficacy, nominal p-values may be reported. Raw data descriptive statistics will also be presented.

Other secondary efficacy and exploratory endpoints for cohort A1 and cohort B1 may also be analyzed by type of endpoint. If the sample size is sufficient, continuous variables will be summarized by the descriptive statistics (e.g., n, mean, SD, Q1, median, Q3, minimum and maximum, etc.). Binary variables will be summarized using the number and percentage of subjects in each treatment group. No statistical hypothesis testing will be performed for cohort A1 and cohort B1. This approach may also be applied to adolescent subjects.

Binary Endpoints

Binary endpoints in cohort A and cohort B will be analyzed by applying the same approach used for the primary efficacy endpoints.

For endpoints regarding viral loads, visits with missing viral load (\log_{10} copies/mL) in NP swab samples will not be included in the analyses. For binary endpoints regarding the index case or household members linkage to R10933-10987-COV-2067 or subjects in cohort B, and endpoints regarding the medically attended visits, Fisher's exact test will be used. KM curves will be used to assess the exploratory endpoint of proportion of baseline-seronegative subjects who have a first RT-qPCR confirmed SARS-CoV-2 infection in the follow-up period.

Continuous Endpoints

The secondary and exploratory continuous efficacy endpoints such as TWA, AUC, and maximum viral load (\log_{10} copies/mL) will be analyzed using the ANOVA including treatment group, region, and age group as fixed effects in the model. The continuous endpoints regarding change from baseline in cohort B (e.g., TWA of change/percent change from baseline) will be analyzed using the ANCOVA model with treatment group, region, and age group as fixed effects, and the relevant baseline values as covariate as well as treatment-by-covariate interaction. The REGN10933+REGN10987 group will be compared to the placebo group and corresponding least square of mean difference, standard error (SE) and 95% confidence interval will be provided. For

other endpoints with non-normal/skewed distribution (e.g. number of days of symptoms (strict-term, and CDC definition, etc.)), Van Elteren test will be used.

5.7.5. Interim Analysis

No interim analysis will be conducted for this study.

5.8. Analysis of Safety Data

The analysis of safety and tolerability will be performed in SAF, as defined in Section 3.2. For each cohort, the safety analysis will also be performed by subject baseline serology status and age group (≥ 12 to <18 years and ≥ 18), respectively.

The safety analysis will be based on the reported AEs and other safety information (clinical laboratory evaluations, and vital signs).

Thresholds for PCSV in laboratory variables, and vital signs are defined in Appendix 10.3.

The summary of AE results will be presented for each treatment group for each of three TEAE periods: treatment-emergent EAP (TEEAP), treatment-emergent follow-up period (TEFUP), and overall study period (i.e., combined across the TEEAP and TEFUP), and by study cohort. For laboratory and vital sign results they will be presented for each treatment group for each of three periods: EAP, follow-up, and overall study period.

General common rules

All safety analyses will be performed, unless otherwise specified, using the following common rules:

- Safety data in subjects who do not belong to the safety analysis set (i.e., exposed but not randomized) will be listed separately.
- PCSV values are those values considered medically important by the Sponsor according to predefined criteria/thresholds based on literature review and defined by the Sponsor for clinical laboratory tests and vital signs (PCSV criteria described in Appendix 10.3). Considering that the threshold defined in the PCSV list for monocytes and basophils can be below the ULN, the following PCSV criterion will be used for the PCSV analysis of monocytes and basophils:
 - PCSV criterion for monocytes: >0.7 Giga/L or $>$ ULN (if ULN ≥ 0.7 Giga/L).
 - PCSV criterion for basophils: >0.1 Giga/L or $>$ ULN (if ULN ≥ 0.1 Giga/L).
- PCSV criteria will determine which subjects had at least 1 PCSV during the respective TEAE periods, taking into account all evaluations including unscheduled or repeated evaluations.
- The treatment-emergent PCSV denominator by treatment group for a given parameter will be based on the number of subjects assessed for that given parameter at least once during the respective TEAE periods.

- All unscheduled measurements will be assigned to Global Analysis Windows defined in [Table 5](#) of Section [6.4](#) in order to provide an assessment for the screening/baseline visit through follow-up visit time points.
- For quantitative safety parameters including central laboratory measurements and vital sign scores, descriptive statistics will be used to summarize observed values and change from baseline values by visit.

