### 9.2.2.3. Assessment of Medically Attended Visits

Only for RT-qPCR positive subjects (cohort A, cohort A1, cohort B, and cohort B1): Subjects and/or their parent/guardian (as appropriate) who are or become SARS-CoV-2 RT-PCR positive will be queried on any SARS-CoV-2 infection-related medically attended visits to the ED, UCC, or hospitalization (Table 3 and Table 5). The assessment of medically attended visits to ED, UCC or hospitalization will be performed from the time the subject first becomes SARS-CoV-2 RT-qPCR positive or from the time they develop symptoms suspected to be COVID-19 (later confirmed by RT-qPCR positive results) until the subject has had 2 negative tests or COVID-19 related symptoms have resolved (whichever lasts longer), or until the end of study visit. Details associated with any SARS-CoV-2 infection-related medically-attended visit will be recorded and will include at minimum:

- Nature of the visit (ED, UCC, hospital stay)
- Date and length of visit
- Primary reason for the visit should be recorded as an adverse event
- Assessment of the following parameters or occurrences (worst or most abnormal finding) during the medically attended visit/stay:
  - Abnormal vital signs: respiratory rate  $\geq 30$  per minute, heart rate  $\geq 125$  per minute, peripheral capillary oxygen saturation ( $\text{SpO}_2$ )  $\leq 93\%$  on room air at sea level, or oxygen partial pressure ( $\text{PaO}_2$ )/fractional inspired oxygen ( $\text{FiO}_2$ )  $< 300$  mm Hg)  
*Note: these limits for abnormal vital signs are for adult and adolescent subjects.*
  - Respiratory failure: needing high-flow oxygen, noninvasive ventilation, mechanical ventilation, extracorporeal membrane oxygenation (ECMO)
  - Evidence of shock: systolic blood pressure (SBP)  $< 90$  mm Hg, diastolic blood pressure (DBP)  $< 60$  mm Hg, or requiring vasopressors  
*Note: these limits for abnormal vital signs are for adult and adolescent subjects.*
  - Multiorgan dysfunction: Significant acute renal, hepatic, or neurologic dysfunction
  - Multisystem inflammatory syndrome in children (MIS-C)  
*Note: for pediatric subjects  $< 18$  years only*
  - Admission to an ICU

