#### **11.4.5.2. Other Safety (Vital Signs and Laboratory Tests)**

##### Definitions

The following definitions will be applied to laboratory parameters and vital signs:

- The potentially clinically significant value (PCSV) criteria are defined as abnormal values considered medically important by the Sponsor according to predefined criteria/thresholds based on literature review and defined by the Sponsor for clinical laboratory tests and vital signs. The PCSV criteria will be provided in the SAP.
- PCSV criteria will determine which subjects had at least 1 PCSV during the respective TEAE periods, taking into account all evaluations performed during the respective TEAE periods, including unscheduled or repeated evaluations. The number of all such subjects will be the numerator for the PCSV percentage.

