3.2. The Safety Analysis Set (SAF)

The safety analysis set (SAF) includes all randomized subjects who received at least 1 dose or part of a dose of study drug. Subjects in the SAF will be analyzed based on the treatment received (as treated). In general, safety will be evaluated by study cohort: SAF-A (Cohort A), SAF-B (Cohort B), SAF-A1(Cohort A1), and SAF-B1 (Cohort B1). However, injection site reactions will also be based on all cohorts combined.

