5.8.3. Analysis of Vital Signs

For the respective EAP, FUP, and overall study period, the vital sign actual values (quantitative) and change from baseline values will be descriptively summarized at baseline and each post-baseline visit will be summarized by treatment group.

Individual subject laboratory parameter measurements will be additionally evaluated by PCSV criteria (See Appendix 10.3), specifically identifying subjects with at least one post-baseline measurement that meets the PCSV criteria.

Subject listings of vital sign measurements that meet PCSV criteria will be provided for the report appendix.

5.8.4. Analysis of Other Safety Variables - Abnormal Findings during SARS-CoV-2 Infection-related Medically Attended Visits

For subjects who become SARS-CoV-2 positive and require medically attended visits to the emergency department (ED), urgent care center (UCC), or hospitalization starting from the timepoint of SARS-CoV-2 RT-qPCR positive and through the end of the study, will have the following parameters or occurrences (worst or most abnormal finding) during the medically attended visit/stay collected (eCRF).

- Nature of visit (ED, UCC, hospital stay)
- Abnormal vital signs: respiratory rate ≥ 30 per minute, heart rate ≥ 125 per minute, peripheral capillary oxygen saturation (SpO_2) $\leq 93\%$ on room air at sea level, or oxygen partial pressure (PaO_2)/fractional inspired oxygen (FiO_2) < 300 mm Hg
- Respiratory failure: needing high-flow oxygen, noninvasive ventilation, mechanical ventilation, extracorporeal membrane oxygenation (ECMO)
- Evidence of shock: systolic blood pressure (SBP) < 90 mm Hg, diastolic blood pressure (DBP) < 60 mm Hg or requiring vasopressors (Note: *these limits for abnormal vital signs are for adult and adolescent subjects.*)
- Multiorgan dysfunction: Significant acute renal, hepatic, or neurologic dysfunction
- Multisystem inflammatory syndrome in children (MIS-C). (Note: for pediatric subjects < 12 years only.)
- Admission to an ICU

Number and percentage of subjects who presented at least one of abnormal findings and then by each of these 5 abnormal findings will be provided by treatment group and TEAE period (TEEAP, TEFUP, and overall study period). Within each abnormal findings, number and percentages of subjects will also be reported for each observed criterion.

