10.3. Criteria for Potentially Clinically Significant Values (PCSV)

Parameter	PCSV For Studies in healthy subjects only	Comments
Clinical chemistry		
ALT	>3 and \leq 5 ULN and baseline \leq 3 ULN >5 and \leq 10 ULN and baseline \leq 5 ULN >10 and \leq 20 ULN and baseline \leq 10 ULN >20 ULN and baseline \leq 20 ULN	Enzymes activities must be expressed in ULN, not in IU/L. Each category is calculated independently.
AST	>3 and \leq 5 ULN and baseline \leq 3 ULN >5 and \leq 10 ULN and baseline \leq 5 ULN >10 and \leq 20 ULN and baseline \leq 10 ULN >20 ULN and baseline \leq 20 ULN	Enzymes activities must be expressed in ULN, not in IU/L. Each category is calculated independently.
Alkaline Phosphatase	>1.5 ULN and baseline \leq 1.5 ULN	Enzymes activities must be expressed in ULN, not in IU/L.
Total Bilirubin	>1.5 and \leq 2 ULN and baseline \leq 1.5 ULN >2 ULN and baseline \leq 2.0 ULN	Must be expressed in ULN, not in μ mol/L or mg/L.
Conjugated bilirubin	>35% Total Bilirubin and TBILI >1.5 ULN, and baseline Total Bilirubin \leq 35% or TBILI \leq 1.5 ULN	Conjugated bilirubin dosed on a case-by-case basis
ALT and Total Bilirubin	ALT >3 ULN and TBILI >2 ULN, and baseline ALT \leq 3 ULN or TBILI \leq 2ULN	
CPK	>3 and \leq 10 ULN and baseline \leq 3ULN >10 ULN and baseline \leq 10ULN	
Creatinine	\geq 150 μ mol/L (Adults) or \geq ULN (if ULN \geq 150 μ mol/L) and baseline $<$ 150 μ mol/L or $<$ ULN (if ULN \geq 150 μ mol/L) \geq 30% change from baseline \geq 100% change from baseline	3 independent criteria
Creatinine Clearance (Cockcroft's formula)	<15 ml/min and baseline \geq 15 ml/min (end stage renal impairment) \geq 15 to <30 ml/min and baseline \geq 30 ml/min (severe renal impairment) \geq 30 to < 60 ml/min and baseline \geq 60 ml/min (moderate renal impairment) \geq 60 to < 90 ml/min and baseline \geq 90 ml/min (mild renal impairment)	Four independent criteria

Parameter	PCSV For Studies in healthy subjects only	Comments
Uric Acid		
Hyperuricemia:	>408 μ mol/L or >ULN (if ULN \geq 408 μ mol/L) and baseline \leq 408 μ mol/L or \leq ULN (if ULN \geq 408 μ mol/L)	Two independent criteria
Hypouricemia:	<120 μ mol/L or <LLN (if LLN \leq 120 μ mol/L) and baseline \geq 120 μ mol/L or \geq LLN (if LLN \leq 120 μ mol/L)	
Blood Urea Nitrogen	\geq 17 mmol/L or \geq ULN (if ULN \geq 17 mmol/L) and baseline <17 mmol/L or <ULN (if ULN \geq 17 mmol/L)	Two independent criteria
Chloride		

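### SAP 5.8.4 drops the protocol's adult/adolescent restriction on abnormal vital signs, and the Appendix 10.3 limits applied to children under 12 have no age bands

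*SAP*

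**What the plan says.** **PCSV.** Protocol 11.4.5.2 leaves the criteria to the SAP: "The PCSV criteria will be provided in the SAP". SAP 5.8 then says "Thresholds for PCSV in laboratory variables, and vital signs are defined in Appendix 10.3", with no limitation by cohort or age. The safety analysis set in SAP 3.2 is evaluated by cohort and includes SAF-A1 and SAF-B1, the children under 12. Appendix 10.3 has one column of limits, headed "PCSV For Studies in healthy subjects only". The only age marker in it is on the absolute creatinine cut-off of 150 µmol/L ("mol/L (Adults) or"), and no paediatric counterpart follows. SAP 4.6.4 applies the ranges as applicable, without defining that phrase.

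**Medically attended visits.** For infected subjects seen in an emergency department, urgent care centre or hospital, Protocol 9.2.2.3 lists findings to record in all four cohorts. Under two of them, abnormal vital signs and evidence of shock, it adds a note that "these limits for abnormal vital signs are for adult and adolescent subjects". SAP 5.8.4 has the same list. Its item beginning "Abnormal vital signs: respiratory rate" carries no such note; its shock item does.

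**The concern.** Safety is a primary objective for A1 and B1, and evaluating it is a stated reason for enrolling them. No hypothesis tests are planned there, so the descriptive safety tables are a main output of these cohorts. If the rules behind those tables are not meant for young children, the counts can mix values that carry no information with values that do, in both arms. In 5.8.4 the problem is also a direct conflict between the two documents, which needs no outside reference range to see: one says the limits are not for children under 12, and the other applies them without restriction.

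**Working it through.** No figure in the plan needs reproducing. The check sets the texts side by side and follows the rules through.

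**1. Medically attended visits**

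| Item | Protocol 9.2.2.3 | SAP 5.8.4 |
|---|---|---|
| Abnormal vital signs: RR ≥30/min, HR ≥125/min, SpO2 ≤93%, PaO2/FiO2 <300 mm Hg | Adults and adolescents only | Same limits, no restriction |
| Evidence of shock | Adults and adolescents only | Adults and adolescents only |
| MIS-C | Under 18 years | Under 12 years |

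Children under 12 are in scope of the SAP list, since its MIS-C item is addressed to them. With the restriction kept on one item and absent from the other, the plain reading is that the vital-sign limits apply to everyone. These limits have no change-from-baseline condition, so nothing softens them. The item also feeds the summary line for subjects with at least one abnormal finding.

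**2. Appendix 10.3, by type of rule**

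- *Multiples of the upper limit of normal (ULN).* ALT, AST, alkaline phosphatase, total bilirubin and CPK. The table insists that "Enzymes activities must be expressed in ULN, not in IU/L". These rules follow the child's age if the laboratory's ULN does; the documents do not say whether it does.
- *Fixed limits with substitution.* For most other laboratory tests the ULN replaces the fixed limit only if it is at or above it, and the lower limit of normal (LLN) only if it is at or below it. The correction works in one direction. A child's creatinine ULN below 150 µmol/L, for example, never replaces 150.
- *Creatinine change.* Rises of ≥30% and ≥100% from baseline are independent criteria, so deterioration below 150 µmol/L is still caught.
- *Heart rate and blood pressure.* Both a limit and a change are required: HR ≥120 with a rise ≥20, or SBP ≤95 with a fall ≥20. HR 105 to 125 (+20) is flagged; 125 to 130 (+5) is not. SBP 115 to 95 (−20) is flagged; 90 to 75 (−15) is not.
- *Missing baseline.* SAP 6.3 says that if the change condition is missing, the threshold decides alone. Protocol 9.2.3.1 has blood pressure taken in children only where feasible for their age, so missing baselines are foreseeable. A later SBP of 90 is then flagged, because 90 ≤ 95, and under 6.3 the child is grouped as normal/missing at baseline.

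**3. Creatinine clearance**

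The table names a weight-based formula but does not print it. I assume its usual form, clearance = (140 − age) × weight × k / creatinine, with k = 1.23 for males and 1.04 for females and creatinine in µmol/L. The creatinine values of 20 to 40 are also assumed.

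- 5 kg, 0.3 years: 139.7 × 5 × 1.23 / 20 = 43 mL/min (boy, creatinine 20), down to 139.7 × 5 × 1.04 / 40 = 18 (girl, creatinine 40).
- 10 kg, 1 year: 139 × 10 × 1.23 / 20 = 85, down to 139 × 10 × 1.04 / 40 = 36.

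These raw values are not PCSVs. Each band also needs a baseline in a better band, so a stable infant at 18 to 43 mL/min meets no criterion. The weakness is at the band edges. For the 5 kg boy, creatinine 28 gives 859.2 / 28 = 30.7, and creatinine 29 gives 859.2 / 29 = 29.6. That crosses 30 and counts as severe impairment on a creatinine rise of 1/28 = 3.6%, far below the table's own 30% criterion. Low body weight puts the infant near that edge.

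**The case against.** A reader might infer that the SAP imposes an adult table that will flag ordinary infant values, miss renal deterioration and corrupt the safety tables of some 250 children. The documents do not support that.

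- The table is labelled for healthy subjects. Only the creatinine cut-off is marked for adults, so calling the whole table adult is an inference. It also lists HbA1c and CRP, which are not among the protocol's laboratory tests, so it looks like a generic template.
- An infant with a steady heart rate of 130 or SBP of 85 is not flagged when a baseline exists, and the enzyme rules scale to the ULN.
- The claim about missed renal deterioration fails on the creatinine change criteria.
- SAP 5.8.4 concerns only infected subjects with medically attended visits, which is a subset. The note's survival under shock, and the statement in SAP 1.2.4 that nothing departs from protocol amendment 6, suggest an editorial omission rather than a decision.
- Observed values and changes are summarised by visit regardless of PCSV, investigators review every laboratory value, and A1 and B1 are reported separately from the adult cohorts.

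All of this stands and limits the harm. It does not remove the conflict in 5.8.4, because programmers work from the text and the text now covers everyone. Nor does it cover the one-way substitution, the clearance bands or the missing-baseline fallback. An undefined qualifier such as as applicable gives no rule for choosing which criteria to use in children.

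**Conclusion.** The concern holds in two limited parts. First, SAP 5.8.4 contradicts Protocol 9.2.2.3 on who the abnormal-vital-signs limits are for. This rests on the text alone, and assumes only that the case report form records the item for children under 12. Second, Appendix 10.3 can misclassify children on some parameters: fixed limits with one-way substitution, creatinine clearance, and blood pressure or heart rate when the baseline is missing.

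The stronger statement, that it will misclassify them, is not supported. The documents contain no paediatric reference ranges and no expected number of medically attended visits in children, so no count can be given. The planned 250 (225 in A1, 25 in B1) is the outer bound for the PCSV tables, and Protocol 6.1.2 allows that number to change. The group exposed to the 5.8.4 error is smaller and of unknown size. The clearance figures depend on the assumed formula and creatinine values, and show how the rule behaves rather than how often it flags. No efficacy result or type I error is affected. It is worth correcting before the database lock because paediatric safety reporting is a main purpose of these cohorts and the correction is cheap.

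**What to change.** 1. In SAP 5.8.4, restore the adult/adolescent-only restriction to the abnormal-vital-signs item so that it agrees with Protocol 9.2.2.3. Reconcile the age in the MIS-C note (under 12 in the SAP, under 18 in the protocol) at the same time.
2. In Appendix 10.3, limit the fixed-threshold criteria and the creatinine-clearance criteria to subjects aged 12 and over.
3. For A1 and B1, have the sponsor define age-appropriate criteria and write them into the SAP. Candidates are the central laboratory's age-specific reference ranges and the change-from-baseline criteria already in the table. The clinical limits themselves are for the sponsor to set; none is proposed here.
4. State in SAP 6.3 that the threshold-only fallback does not apply to A1 and B1.

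The cost is SAP text and programming. No new data are needed from subjects; if age-specific reference ranges are chosen, they have to be obtained from the central laboratory.

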5.8.1. Adverse Events

All AEs reported in this study will be coded using the currently available version of the Medical Dictionary for Regulatory Activities (MedDRA®). The preferred term (PT), and the primary system organ class (SOC) will be listed.

The number and percentage of subjects with TEAEs will be summarized by treatment group. Summaries will include:

- Overview of TEAEs, i.e., overall number (%) of subjects with any TEAE, Serious TEAE, TEAE leading to death, TEAE leading to study drug withdrawn, or subjects with any COVID-19 TEAE or asymptomatic COVID-19 TEAE
- Overview of non-COVID TEAEs (excluding COVID-19 and asymptomatic COVID-19), i.e., overall number (%) of subjects with any TEAE, Serious TEAE, TEAE leading to death, or TEAE leading to study drug withdrawn
- Overview of AESI, i.e., overall number (%) of subjects with any AESI, grade 3 or greater injection site reactions, grade 3 or greater hypersensitivity reactions, AESI leading to death, or AESI leading to study drug withdrawn)
- TEAEs by primary SOC and PT
- Number of subjects experiencing common TEAE(s) by primary SOC and PT (PT incidence $\geq 5\%$ in any treatment group)
- TEAEs by severity (according to the grading scale outlined in section [10.2.4](#) of the protocol), presented by primary SOC and PT
- TEAEs by relationship to treatment (related, not related), presented by primary SOC and PT
- Treatment-emergent SAEs by primary SOC and PT
- Treatment-emergent AESIs by primary SOC and PT
- TEAEs leading to study drug withdrawn by primary SOC and PT
- Treatment-emergent AESIs leading to study drug withdrawn by primary SOC and PT
- Treatment-emergent AESIs by severity, presented by primary SOC and PT
- Number of subjects who died during TEEAP, TEFUP, and the study period, respectively, and reason for death
- TEAEs leading to death (death as an outcome on the AE CRF page, as reported by the Investigator) by SOC and PT

- AESIs leading to death (death as an outcome on the AE CRF page, as reported by the Investigator) by SOC and PT.

In addition, the number (%) of subjects with any post-baseline fever reported from the fever assessment eCRF, any subject self-recorded symptoms assessment collected in the COVID-19 symptoms assessment eCRF will be summarized by treatment group. The descriptive statistics of the duration (days) of each COVID-19 symptom will also be presented. Subject listing of COVID-19 symptoms including the details such as the start date, end date, and duration of each symptom will be provided. In addition, subject listing of SAEs, AESI, TEAEs related to study drug, and TEAEs leading to study drug withdrawn will also be presented.

